#### **Secondary Objectives**

The secondary objectives are:

- To evaluate preliminary efficacy, including ORR and progression-free survival (PFS)
- To evaluate the minimal residual disease (MRD) negative rate
- To evaluate the PK and immunogenicity of daratumumab
- To assess the safety profile of daratumumab given in 3 different dosing schedules
- To determine if daratumumab has an effect on QT interval

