### **Rationale for QTc Study**

In addition to expression on immune cell populations, CD38 is also expressed on cardiomyocytes. Daratumumab inhibits the cyclase activity of CD38, which is involved in the modulation of ER calcium release. The resulting lower intracellular calcium concentrations could potentially affect the function of cardiomyocytes.

In a limited toxicology study in chimpanzees, no ECG findings were noted. No other cardiovascular safety pharmacology data are available, and generation of further nonclinical safety data would be challenging given the lack of suitable animal models other than the chimpanzee,

since daratumumab does not bind to CD38 of species typically used for nonclinical toxicology testing (mouse, rat, rabbit, pig, cynomolgus monkey, or rhesus monkey).

Preliminary clinical data from study GEN501 Part 2 showed that QTc prolongation was observed upon administration of daratumumab at 16 mg/kg; however, these were not time-matched observations. The pre-to-post dosing increase for QTcF was approximately 10 msec. No subject had a post-dose absolute QT above 500 msec and no subject had an increase from baseline that was more than 60 msec. In addition, no infusion-related cardiac arrhythmia was observed.

To further investigate the potential effect of daratumumab on QTc prolongation, a QTc substudy will be included in this study. This study is suitable for evaluation of QTc since daratumumab is given as a single agent in a relatively healthy population of SMM patients.

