### 11.2. Sample Size Determination

Two hypotheses will be tested:

1.  $H_0$ : CR rate  $\leq 15\%$   
 $H_a$ : CR rate  $\geq 35\%$
2.  $H_0$ : PD/death rate  $\geq 0.346/\text{patient-year}$  (median PFS  $< 24$  months)  
 $H_a$ : PD/death rate  $\leq 0.185/\text{patient-year}$  (median PFS  $> 45$  months)

This study will enroll 120 subjects (40/arm) in total. With 40 subjects per arm, each arm will have:

- 90% power to show that the true CR rate is 35% at a one-sided level of 0.05
- 80% power to show that the true PD/death rate is 0.185/patient year at a one-sided level of 0.1

If two or more treatment schedules are deemed to be effective, with 40 subjects per arm this study would have:

- 85% probability of identifying the arm with the higher CR
- 80% probability of identifying the arm with the lower PD/death rate

For the QTc substudy, assuming that the intrasubject standard deviation for change from baseline in QTc ( $\Delta\text{QTc}$ ) is 20 milliseconds and that the true difference in means is 5 milliseconds, a sample size of 25 evaluable subjects (completers) will have 80% power to show that the upper limit of the two-sided 90% confidence interval (1 sided upper 95% confidence interval) for the difference in mean QTc ( $\Delta\text{QTc}$ ) at each timepoint and baseline will be less than 20 milliseconds. To ensure 25 subjects are evaluable, the QTc substudy will enroll approximately 30 subjects.

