### ECG Analysis

QT interval corrected for heart rate using Fridericia's (QTcF) and Bazett's (QTcB) formulae will be calculated. Descriptive statistics of QTc intervals and changes from baseline will be summarized at each scheduled timepoint. A mixed effects analysis of variance (ANOVA) model will be fit with QTc as the dependent variable, scheduled timepoint of measurement as the fixed effect, and subject as a random effect. Using the means and intrasubject variance obtained from this model, 2 sided 90% confidence intervals will be calculated for the difference in the mean QTc

from baseline at each scheduled timepoint. An effect on QTc will be ruled out if the upper bound of the 90% confidence interval for the difference in means between the postbaseline QTc (at each timepoint) and baseline QTc is less than 20 milliseconds.

The proportion of subjects with a post-dose QTc interval >450 milliseconds and >480 milliseconds will be summarized, as will the proportion of subjects with QTc interval increases from baseline >30 milliseconds or >60 milliseconds. A listing of subjects with a QTc interval >500 milliseconds will also be provided.

The proportion of subjects with post-dose PR interval >200 milliseconds, QRS >110 milliseconds, and heart rate >100 bpm and <50 bpm will be reported. The proportion of subjects with ST segment and T and U wave abnormalities will be reported.

All important abnormalities in ECG waveform that are changes from the baseline readings will be reported (eg, changes in T-wave morphology or the occurrence of U waves).

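### The QTc rule says an effect is ruled out when the upper 90% bound is below 20 ms, but that excludes only mean increases of 20 ms or more, not the roughly 10 ms seen before the substudy

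*Protocol*

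**What the plan says.** The secondary objective (Protocol Section 2.1, repeated in SAP Section 1.1) is unqualified: "To determine if daratumumab has an effect on QT interval". The decision rule in Protocol Section 11.8, ECG Analysis, reads "An effect on QTc will be ruled out if the upper" bound of the 90% interval for the difference in means "between the postbaseline QTc (at each timepoint) and baseline QTc is less than 20 milliseconds".

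Section 11.2 expresses the target more neutrally. It asks that the "upper limit of the two-sided 90% confidence interval (1 sided upper 95% confidence interval") be under 20 ms, and takes 20 ms as the "intrasubject standard deviation for change from baseline in QTc". It assumes that the "true difference in means is 5 milliseconds", and says that "a sample size of 25 evaluable subjects (completers) will have 80% power". SAP Section 1.4 repeats this.

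The background in Section 3.2 (Rationale for QTc Study) is a mechanistic concern plus an observation from an earlier study: "The pre-to-post dosing increase for QTcF was approximately 10 msec". The protocol says that those readings were not time-matched. Neither document justifies 20 ms as the margin. SAP Section 1 assigns the QTc analysis and reporting to an external vendor and gives no other rule, so Section 11.8 holds the only QTc decision rule in the two documents.

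**The concern.** An upper confidence bound below 20 ms supports one statement: the mean increase is less than 20 ms. It does not support the statement that there is no effect. Section 11.8 moves from the first to the second, and the second reads as a direct answer to the objective.

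The gap matters because the margin is twice the earlier observation of about 10 ms. A true increase of that size can meet the criterion, and so can data whose interval excludes zero. Followed literally, the rule could attach a conclusion of no QTc effect to results that show an increase, in asymptomatic subjects whose tolerance for a cardiac safety risk is low.

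**Working it through.** **Inputs.** From Section 11.2: 25 completers (about 30 enrolled), 20 ms standard deviation, 5 ms assumed true difference, two-sided 90% interval. From Section 11.8: 20 ms margin. From Section 3.2: about 10 ms, used here as an assumed true increase. The 0.95 quantile of t on 24 degrees of freedom is 1.711.

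**Formula.** A timepoint passes if mean + 1.711 × SE < 20. For a true increase d, the pass probability is P(T < −1.711), where T is noncentral t on 24 df with noncentrality (d − 20)/SE.

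**Step 1: the plan's own figure (d = 5).** The 20 ms can be read in two ways.

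- *SD of the change, as literally worded.* SE = 20/√25 = 4; noncentrality −15/4 = −3.75; power 0.977. Only 13 subjects would be needed for 80%.
- *SD of a single reading.* SD of change = 20√2 = 28.3; SE = 28.3/5 = 5.66; noncentrality −15/5.66 = −2.65; power 0.824. The smallest n for 80% is 24.

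The second reading roughly reproduces 25 subjects at 80% power and the first does not. It also fits Section 11.8, which takes the intrasubject variance from a model for QTc itself. Because the wording supports the first reading, both are carried forward.

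**Step 2: largest observed mean that passes, at the assumed SD.** 20 − 1.711 × 4 = 13.2 ms, or 20 − 1.711 × 5.66 = 10.3 ms. An observed 10 ms passes under either reading. With SE 4, an observed 12 ms gives 12 ± 6.8, that is 5.2 to 18.8 ms. Zero is excluded, yet the rule says that an effect is ruled out.

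**Step 3: pass probability at one timepoint.**

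| True increase | n | SD of change 20 | SD of change 28.3 |
|---|---|---|---|
| 0 ms | 25 | 0.999 | 0.963 |
| 10 ms | 25 | 0.783 | 0.529 |
| 10 ms | 30 | 0.848 | 0.597 |

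At 10 ms and n = 25 the noncentralities are −10/4 = −2.5 and −10/5.66 = −1.77. Pooling degrees of freedom across timepoints in the mixed model changes little: the normal-theory limits are 0.80 and 0.55.

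**Step 4: interval wholly above zero and rule still met (true 10 ms, n = 25, one timepoint, by simulation).** 0.57 with SD of change 20 and 0.11 with 28.3. The second is small because the half-width is about 1.711 × 5.66 = 9.7 ms. At that width, only observed means between about 9.7 and 10.3 ms fit the interval between 0 and 20.

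**Step 5: all timepoints required.** Section 9.5.1 gives four ECG timepoints after daratumumab has started: end of infusion at Dose 1; and pre-dose, end of infusion and one hour later at Dose 8. Suppose that each carries a 10 ms increase, reading errors are independent and all four must pass. By simulation:

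| Baseline | SD of change 20 | SD of change 28.3 |
|---|---|---|
| One shared baseline | 0.53 | 0.22 |
| Separate time-matched baseline for each | 0.38 | 0.08 |

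**The case against.** The strongest reply is that the results will speak for themselves. Section 11.8 already plans mean changes and 90% intervals at each scheduled timepoint, proportions with increases above 30 and 60 ms, and a listing of values above 500 ms. Section 11.6 adds concentration-QTc modelling. An increase would be visible to a careful reader. That stands, and it means that no extra reporting of intervals is needed. It does not change the prespecified conclusion, which is what a summary will carry, and counts above 30 or 60 ms do not address a mean shift of 10 ms.

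Two stronger readings are tempting, and the documents do not support either.

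- *A reader might infer that the rule would usually report no effect in the face of a true 10 ms increase.* The high figure of 0.78 needs the SD reading that implies 97.7% power at 5 ms rather than the stated 80%. Under the reading that roughly reproduces the sample size, the chance is 0.53, close to even. If every timepoint must pass, it can be as low as 0.08. Nor can the documents show what was concluded, since the vendor's plan is not among them.
- *A reader might infer that the upper bound ought to be below 10 ms.* Neither document sets such a criterion, the 10 ms observation was not time-matched, and the substudy was not sized for it. At a true zero effect the gap to a 10 ms bound is again 10 ms, so the probabilities in step 3 apply: the bound would be met only 53% to 78% of the time.

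**Conclusion.** Wrong as written. The defect is in the inference and does not depend on any simulation: a bound below 20 ms cannot exclude an effect, only a mean increase of 20 ms or more.

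The calculations show that the gap is of practical size. At a true 10 ms with 25 subjects, the criterion is met with probability about 0.53 to 0.78 per timepoint, and about 0.08 to 0.53 if four affected timepoints must all pass. In about 11% to 57% of cases per timepoint, the 90% interval would exclude zero while the rule still declares an effect ruled out.

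These figures rest on 10 ms being the true increase, which the documents do not establish. They also rest on one or other reading of the 20 ms SD and, for the joint figures, on independent reading errors, the choice of baseline, and reading the rule as requiring every timepoint to pass.

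**What to change.** In Section 11.8, and in the external vendor's QTc analysis and report, state the conclusion as: *a mean QTc increase of 20 ms or more will be ruled out*. Add that no conclusion of no effect will be drawn at any timepoint where the lower 90% bound is above zero. The upper bound may be discussed descriptively against the earlier observation of about 10 ms, but no 10 ms pass/fail criterion should be added.

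Table 2 notes that the substudy was considered complete as of Amendment 4, so the change applies to how results are concluded and reported. If a report has already been issued, its conclusion should be checked against this wording. The change needs two sentences and no new ECGs or subjects. The cost is a narrower claim.

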### **11.9. Interim Analysis**

There will be one interim analysis for efficacy. This analysis will occur 6 months after the last subject has been randomized. The purpose of this analysis is to make a decision to go forward into Phase 3 based on the analysis of the primary endpoint of CR.

## **12. ADVERSE EVENT REPORTING**

Timely, accurate, and complete reporting and analysis of safety information from clinical studies are crucial for the protection of subjects, investigators, and the sponsor, and are mandated by regulatory agencies worldwide. The sponsor has established Standard Operating Procedures in conformity with regulatory requirements worldwide to ensure appropriate reporting of safety information; all clinical studies conducted by the sponsor or its affiliates will be conducted in accordance with those procedures.

### **12.1. Definitions**

#### **12.1.1. Adverse Event Definitions and Classifications**

##### **Adverse Event**

An adverse event is any untoward medical occurrence in a clinical study subject administered a medicinal (investigational or non-investigational) product. An adverse event does not necessarily have a causal relationship with the treatment. An adverse event can therefore be any unfavorable and unintended sign (including an abnormal finding), symptom, or disease temporally associated with the use of a medicinal (investigational or non-investigational) product, whether or not related to that medicinal (investigational or non-investigational) product. (Definition per International Council on Harmonisation [ICH])

This includes any occurrence that is new in onset or aggravated in severity or frequency from the baseline condition, or abnormal results of diagnostic procedures, including laboratory test abnormalities.

Note: The sponsor collects adverse events starting with the signing of the ICF (refer to Section 12.3.1, All Adverse Events, for time of last adverse event recording).

### **Serious Adverse Event**

A serious adverse event based on ICH and EU Guidelines on Pharmacovigilance for Medicinal Products for Human Use is any untoward medical occurrence that at any dose:

- Results in death
- Is life-threatening  
(The subject was at risk of death at the time of the event. It does not refer to an event that hypothetically might have caused death if it were more severe.)
- Requires inpatient hospitalization or prolongation of existing hospitalization
- Results in persistent or significant disability/incapacity
- Is a congenital anomaly/birth defect
- Is a suspected transmission of any infectious agent via a medicinal product
- Is Medically Important\*

\*Medical and scientific judgment should be exercised in deciding whether expedited reporting is also appropriate in other situations, such as important medical events that may not be immediately life threatening or result in death or hospitalization but may jeopardize the subject or may require intervention to prevent one of the other outcomes listed in the definition above. These should usually be considered serious.

If a serious and unexpected adverse event occurs for which there is evidence suggesting a causal relationship between the study treatment and the event (eg, death from anaphylaxis), the event must be reported as a serious and unexpected suspected adverse reaction even if it is a component of the study endpoint (eg, all-cause mortality).

### **Unlisted (Unexpected) Adverse Event/Reference Safety Information**

An adverse event is considered unlisted if the nature or severity is not consistent with the applicable product reference safety information. For daratumumab, the expectedness of an adverse event will be determined by whether or not it is listed within the Reference Safety Information included in the Investigator's Brochure.

### **Adverse Event Associated with the Use of the Drug**

An adverse event is considered associated with the use of the drug if the attribution is possible, probable, or very likely by the definitions listed in Section 12.1.2.

### **12.1.2. Attribution Definitions**

#### **Not Related**

An adverse event that is not related to the use of the drug.

#### **Doubtful**

An adverse event for which an alternative explanation is more likely, eg, concomitant drug(s), concomitant disease(s), or the relationship in time suggests that a causal relationship is unlikely.

#### **Possible**

An adverse event that might be due to the use of the drug. An alternative explanation, eg, concomitant drug(s), concomitant disease(s), is inconclusive. The relationship in time is reasonable; therefore, the causal relationship cannot be excluded.

#### **Probable**

An adverse event that might be due to the use of the drug. The relationship in time is suggestive (eg, confirmed by dechallenge). An alternative explanation is less likely, eg, concomitant drug(s), concomitant disease(s).

#### **Very Likely**

An adverse event that is listed as a possible adverse reaction and cannot be reasonably explained by an alternative explanation, eg, concomitant drug(s), concomitant disease(s). The relationship in time is very suggestive (eg, it is confirmed by dechallenge and rechallenge).

### **12.1.3. Severity Criteria**

The severity assessment for an adverse event or serious adverse event should be completed using the NCI-CTCAE Version 4.

The investigator should use clinical judgment in assessing the severity of events not directly experienced by the subject (eg, laboratory abnormalities).

## **12.2. Special Reporting Situations**

Safety events of interest on a sponsor study drug that may require expedited reporting and/or safety evaluation include, but are not limited to:

- Overdose of a sponsor study drug. No MTD has been reached for daratumumab. However, if the dose for IV subjects exceeds the maximum tested dose of 24 mg/kg, then it will be considered as overdose in this study.
- Suspected abuse/misuse of a sponsor study drug
- Inadvertent or accidental exposure to a sponsor study drug
- Medication error involving a sponsor product (with or without subject exposure to the sponsor study drug, eg, name confusion)

Special reporting situations should be recorded in the eCRF. Any special reporting situation that meets the criteria of a serious adverse event should be recorded on the adverse event page of the eCRF.

### **12.3. Procedures**

#### **12.3.1. All Adverse Events**

All adverse events and special reporting situations, whether serious or non-serious, will be reported from the time a signed and dated ICF is obtained until 30 days after the last dose of study treatment, unless the subject withdraws consent for study participation, or starts subsequent anticancer therapy. For subjects who have received subsequent treatment with therapeutic intent for MM during the adverse event reporting period, only adverse events that are considered to be possibly, probably, or definitely related to daratumumab need to be reported. Serious adverse events, including those spontaneously reported to the investigator within 30 days after the last dose of study treatment, must be reported using the Adverse Event Form. The sponsor will evaluate any safety information that is spontaneously reported by an investigator beyond the time frame specified in the protocol.

Disease progression should not be recorded as an adverse event or serious adverse event term; instead, signs and symptoms of clinical sequelae resulting from disease progression/lack of efficacy will be reported if they fulfill the serious adverse event definition (refer to Section 12.1.1). Death should not be recorded as an adverse event or serious adverse event, but as the outcome of an adverse event. The adverse event that resulted in the death should be reported as a serious adverse event. All events that meet the definition of a serious adverse event will be reported as serious adverse events, regardless of whether they are protocol-specific assessments.

All adverse events, regardless of seriousness, severity, or presumed relationship to study treatment, must be recorded using medical terminology in the source document and the eCRF. Whenever possible, diagnoses should be given when signs and symptoms are due to a common etiology (eg, cough, runny nose, sneezing, sore throat, and head congestion should be reported as "upper respiratory infection"). Investigators must record in the eCRF their opinion concerning the relationship of the adverse event to study therapy. All measures required for adverse event management must be recorded in the source document and reported according to sponsor instructions.

The sponsor assumes responsibility for appropriate reporting of adverse events to the regulatory authorities. The sponsor will also report to the investigator (and the head of the investigational institute where required) all serious adverse events that are unlisted (unexpected) and associated with the use of the study drug. The investigator (or sponsor where required) must report these events to the appropriate Independent Ethics Committee/Institutional Review Board (IEC/IRB) that approved the protocol unless otherwise required and documented by the IEC/IRB.

Subjects (or their designees, if appropriate) will be provided with a "wallet (study) card" and instructed to carry this card with them for the duration of the study indicating the following:

- Study number
- Statement, in the local language(s), that the subject is participating in a clinical study
- Investigator's name and 24-hour contact telephone number
- Local sponsor's name and 24-hour contact telephone number (for medical staff only)
- Site number
- Subject number
- Blood type and IAT (as described in Section 9.5.2)

